6. STUDY TREATMENT

6.1. General Information

Study treatments are summarized in Table 3.

Table 3: Study Treatments

Group Name	NBI-921352	Placebo
Doses	Subjects will receive up to 4 dose levels during the study based on their assigned weight group. [REDACTED]	Placebo is administered in the same manner and on an identical schedule as NBI-921352.
Unit Dose Strengths	[REDACTED]	Placebo
Dose Formulation	[REDACTED]	Matching oral granules in sprinkle capsules
Route of Administration	Oral or G-tube	Oral or G-tube
Sourcing	Provided centrally by the Sponsor	Provided centrally by the Sponsor
Packaging and Labeling	Study treatment will be provided [REDACTED]	Matching placebo will be provided [REDACTED]

tid=3 times a day; WG=weight group.

6.2. Study Treatment Administration

the first time in the history of the world, the people of the United States have been called upon to determine whether they will submit to the law of force, and give up the God-given right of self-government, or whether they will, in the language of their ancestors, stand by their principles and "die freemen rather than live slaves."

6.3. Study Treatment Storage and Compliance

The designated personnel is responsible for maintaining records of the quantity and dates of all study treatment supplies received, dispensed, returned, lost, and destroyed, according to applicable regulations and study procedures. Study treatment should be stored in a locked area accessible only to the designated pharmacist or qualified personnel. A detailed description of how study treatment should be dispensed, stored, and reconstituted, and any stability changes will be provided in the Pharmacy Manual.

6.4. Study Treatment Accountability and Return

Parents/caregivers will bring all unused study treatment and empty packaging material to the center at specified study visits for drug accountability and reconciliation by study center personnel. A compliance check will be performed by counting the capsules returned at each study visit.

The quantity of study treatment dispensed, used, and returned will be recorded on a dispensing log or otherwise documented. The quantity of study treatment lost or destroyed must also be accounted for and documented. The designated pharmacist or qualified personnel will be responsible for maintaining accurate records of the quantity and dates of all study treatment supplies received, dispensed, and returned.

Returns will be shipped to NBI or its designee at the completion of the study according to instructions provided by NBI or its designee according to applicable local and national regulations and study procedures.

6.5. Direct-to-Subject Shipments of Study Treatment

To ensure continued access to study treatment, if a subject is unable to go to the site when study treatment is to be dispensed, study treatment may be delivered from the site's pharmacy to the subject's residence by a distributor independent from the Sponsor. The subject's name, address, and other contact details will not be accessible to the Sponsor, and the distributor will not have access to the subject's health information.

6.6. Blinding

This is a double-blind, placebo-controlled study during which the subject, parent/caregivers, investigator, all study center personnel, and the Sponsor, with the exception of clinical trial material supply chain personnel who do not have access to study data and are not involved in decisions regarding subject's treatment, will be blinded to the subject's treatment assignment (NBI-921352 or placebo).

The randomization code will be broken for an individual subject only if the subject is pregnant, experiences a serious adverse event (SAE) that the investigator feels cannot be adequately treated without knowing the subject's treatment assignment, or for regulatory reporting requirements. In the case of a medical emergency in which knowledge of the identity of the study treatment is important for subject management, the investigator has the responsibility to decide whether to break the blind; treatment assignments will be unblinded following the interactive web response system (IWRS) process. It is recommended that the investigator contact

the Study Medical Monitor (or designee) before unblinding the treatment assignment if it would not result in unnecessary delay to the immediate medical management of the subject. The investigator must document the date, time, and the reason the blind was broken.

Members of the DMC, the independent statistics group that generates the DMC reports, and the pharmacokineticist providing the PK analysis for the Sentinel Cohort will be unblinded throughout the study.

6.7. Procedures for Overdose

For this study, any dose of NBI-921352 greater than the subject's assigned dose level within a 24-hour time period will be considered an overdose. The current version of the Investigator's Brochure should be referenced for overdose information. There is no recommended specific treatment for an overdose but to provide supportive care if clinically indicated.

In the event of a suspected overdose, the investigator and/or treating physician should:

1. Closely monitor the subject for any AE/SAE and laboratory abnormalities and follow the AE reporting process. The Study Medical Monitor should be contacted for adverse events related to an overdose.
2. Document the quantity of the excess dose(s), as well as the date(s) on which the additional dose(s) were taken, if this information is available.

Subjects who overdose will be counseled on correct dosing and administration of study treatment. Decisions regarding study discontinuation, dose interruptions, or dose modifications will be made by the investigator in consultation with the Medical Monitor based on the clinical evaluation of the subject.

7. SUBJECT RESTRICTIONS

7.1. Prior and Concomitant Medications

All prescription and over-the-counter medications, dietary supplements (including vitamins), and herbal supplements taken by the subject within 30 days before screening will be recorded on the Prior and Concomitant Medications page of the eCRF. All previously taken ASMs and reasons for discontinuation will also be recorded on a separate eCRF.

The following medications are prohibited for all subjects beginning 30 days before the screening visit (unless otherwise stated) until the final study visit (or upon early discontinuation of study treatment):

- Cannabinoids or medical marijuana except Epidiolex/Epidyolex, unless approved by the Sponsor.
- Systemic steroids (eg, high dose prednisolone, ACTH) are prohibited for at least 3 months before the screening visit. Inhaled steroids for asthma treatments and intermittent steroids to treat nonepilepsy related diseases (such as allergies or dermatological conditions) are allowed.

- Any investigational treatments received in the context of a clinical study, unless approved by Sponsor.

ASMs must be stable throughout the study.

Rescue Medication

Subjects must have an adequate rescue medication regimen in place for the duration of the study. Short-term benzodiazepines may be used as acute treatment for prolonged seizures. If needed, longer-acting ASMs may be used as rescue medication based on the investigator's discretion. Rescue medication is permitted at any time and will not be a reason for discontinuation from study treatment; however, use of rescue medication will be collected in the seizure diary and must be documented in the eCRF.

7.2. Dietary and Other Restrictions

Subjects who are on a ketogenic diet must have started the diet at least 30 days prior to screening and diet must remain stable throughout the study. If using VNS, subjects must have stable settings for at least 30 days before screening and throughout the study.

8. DISCONTINUATION OF STUDY TREATMENT AND SUBJECT WITHDRAWAL

Subjects can discontinue study treatment or withdraw their consent to participate in the study at any time. The investigator must discontinue study treatment dosing or withdraw any subject from the study at the parent/caregiver or subject's request. All subjects discontinuing study treatment dosing should continue study participation for safety and efficacy assessments through the end of Week 16, after which they will be withdrawn.

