Approximately 44 subjects will be randomized into the Main Cohort in a 1:1 ratio (NBI-921352:placebo). Beginning on Day 1, subjects will receive Dose Level 1 for their assigned weight group (based on weight at the screening visit). The titration period will include [REDACTED] at Dose Level 1, [REDACTED] at Dose Level 2, [REDACTED] at Dose Level 3, and [REDACTED] at Dose Level 4, with subjects receiving the dose for their weight group at each dose level as indicated in Table 1, or as determined based on the results of the Sentinel Cohort data review by the DMC.

After [REDACTED] of the titration period, the investigator may decrease a subject's dose to the lower tolerated dose level based on safety and tolerability. Subjects who are unable to escalate to or tolerate Dose Level 2 should be discontinued from study treatment.

Maintenance Period – Sentinel and Main Cohorts

Subjects in both cohorts who complete the titration period will enter the [REDACTED] maintenance period. During the maintenance period, subjects will continue to receive their final tolerated dose from the titration period. Dose levels should not be changed during the maintenance period without prior Sponsor approval. Rescue medication is permitted at any time during the study and will not be a reason for discontinuation from study treatment; however, use of rescue medication will be collected in the seizure diary and must be documented in the electronic case report form (eCRF).

Subjects receiving Dose Levels 3 or 4 who discontinue study treatment at any time before the end of Week 16, including during the titration period, should undergo dose de-escalation if appropriate, during which the subject's current dose will be reduced in a step-wise manner over a period of up to [REDACTED]. Instructions for dose de-escalation will be provided. Subjects who withdraw from the study will not be replaced. Subjects receiving Dose Levels 1 or 2 who discontinue study treatment do not require dose de-escalation.

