Safety	A TEAE is an adverse event that started or worsened in severity following the first dose of study treatment. Subject incidence of TEAEs, serious TEAEs, TEAEs leading to discontinuation of study treatment, fatal TEAEs, and adverse events of special interest will be summarized for each treatment group by system organ class and preferred term. Clinical laboratory, vital signs, ECG, weight, height/length, Tanner stage, C-SSRS, [REDACTED] at baseline and during treatment, and the changes from baseline, will be summarized for each treatment group using descriptive statistics. The incidence of potentially clinically significant laboratory values will be provided. Categorical shift tables for selected laboratory values may also be presented.
PK	The plasma concentration data for NBI-921352 and metabolites will be summarized by sampling time point using the PK Analysis Set. [REDACTED]

ASM=antiseizure medication; BLQ=below the level of quantification; C-SSRS=Columbia-Suicide Severity Rating Scale; ECG=electrocardiogram; PK=pharmacokinetics; SAP=statistical analysis plan; TEAE=treatment-emergent adverse event; VABS-3=Vineland Adaptive Behavioral Scales-3.

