7. SAFETY

Safety and tolerability of NBI-921352 in the Sentinel Cohort will be evaluated by assessment of treatment-emergent adverse events (TEAEs) and SAEs. Data from other safety evaluations (eg, vital signs, physical and neurological examinations, pubertal maturation staging, electrocardiograms, clinical laboratory assessments, Columbia-suicide severity rating scale) will not be summarized. Any abnormal results or significant changes from baseline will be assessed for AE reporting by the investigator and will be captured in the AE summaries.

All outputs for safety endpoints will be based on the safety analysis set. The analysis of the safety data will be based on descriptive statistics and presented by treatment group according to the study visit unless otherwise noted. Safety data will not be subject to any imputation and will be summarized on an observed case basis. No formal hypothesis-testing analysis of safety data will be performed.

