7.1. Adverse Events

A TEAE is an AE with an onset date and time on or after the date of the first dose of study drug and within the 14 days after the date of the last dose of study drug. If the AE onset date and time are unknown, it will be assumed that the AE is a TEAE. If the AE onset time is unknown but the AE onset date is the same date as the first dose of study drug, it will be assumed that the AE is a TEAE. See details for imputing missing/partial start dates (Section 4.3.4.1).

TEAEs, categorized by MedDRA system organ class (SOC) and/or preferred term (PT), will be summarized in frequency tables. The frequency tables will include the number and percentage of unique subjects experiencing each event one or more times by treatment group.

An overall summary table will be provided which summarizes the number and percentage of unique subjects with any TEAE, treatment-emergent SAE, TEAE leading to study drug dose reduction, TEAE leading to study drug withdrawn, TEAE leading to study discontinuation, and TEAE resulting in death. The summary table will also include the frequency distribution of the maximum TEAE intensity (mild, moderate, severe) reported for each subject.

The following summary tabulations will also be presented by treatment group. Unless otherwise noted, the tables will be sorted in alphabetical order. The first line of the table will display the number and percentage of subjects with at least one of the following adverse event categories:

- TEAEs, classified by SOC and PT
- Any TEAEs, classified by PT, displayed in a descending order by frequency in the NBI-921352 group
- Treatment-emergent SAEs by SOC and PT
- TEAEs leading to study drug withdrawn by SOC and PT
- TEAEs leading to study discontinuation by SOC and PT
- TEAEs leading to death by SOC and PT

Separate listings of TEAEs resulting in study drug dose reductions, SAEs, and fatal AEs will also be provided. In the event that no subjects experience study drug dose reductions, SAEs, or

fatal AEs, the blank listing shell will be presented with text printed in the center of the listing describing that no adverse events of that type occurred during this study.

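### SAP 7.1 ends the TEAE period 14 days after the last dose without declaring the change from the protocol, so later non-serious AEs have no named output

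*Protocol*

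**What the plan says.** **Definition.** Protocol Table 9 (section 11.4): "A TEAE is an adverse event that started or worsened in severity following the first dose of study treatment". No end date is given. SAP 7.1 requires onset on or after the date of first dose and "within the 14 days after the date of the last dose of study drug". It adds a rule for undated events: "If the AE onset date and time are unknown, it will be assumed that the AE is a TEAE".

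**Collection.** Protocol 8 says that subjects who stop dosing "should continue study participation for safety and efficacy assessments through the end of Week 16". Protocol 8.1 counts their safety follow-up among the data it is important to obtain. Protocol 10 records AEs from consent to the final visit or early termination.

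**Output.** The AE tables in SAP 7.1 cover TEAEs and treatment-emergent SAEs, and include "TEAEs leading to study discontinuation by SOC and PT". For listings it says: "Separate listings of TEAEs resulting in study drug dose reductions, SAEs, and fatal AEs will also be provided". SAP 7 leaves laboratory, ECG, vital-sign and other safety data unsummarised, on the ground that abnormal results are assessed for AE reporting and "will be captured in the AE summaries".

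**Declared changes.** SAP 9 declares the restriction to the Sentinel Cohort, a selected set of safety data, a synoptic report and no efficacy analysis. It does not mention the TEAE definition.

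**The concern.** The protocol asks families to stay in safety follow-up after the drug is stopped, and the SAP then provides no display for part of what that follow-up yields. AE summaries carry the whole weight of safety reporting in this SAP. The study was terminated and the Main Cohort was never enrolled, so no later cohort in this study can fill the gap. With 4 subjects planned per arm, a single subject is 25% of an arm.

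Two things are at stake. First, a reader of the report alone may take the TEAE counts to follow the protocol's definition. Second, a new non-serious event or abnormality that first appears more than two weeks off drug would not be reported, even if it led the subject to leave the study.

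**Working it through.** No figure in the plan is to be reproduced. The check is a comparison of texts followed by day arithmetic.

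**Step 1: where each kind of post-drug AE would appear under SAP 7.1.**

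| AE starting after the last dose | Named table | Named listing |
|---|---|---|
| Within 14 days | Yes, as a TEAE | Depends on type |
| Onset unknown | Yes, assumed a TEAE | Depends on type |
| After 14 days, serious or fatal | No | Yes; these listings are not worded as treatment-emergent only |
| After 14 days, non-serious, onset known | No | No |

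Only the last row is without an output. SAP 4.1 promises that all available data go into relevant displays, but SAP 7.1 names no display for that row.

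**Step 2: what this does to SAP 7's reliance on AE summaries.** An abnormality reported as an AE that began inside the window is counted, even if it persists. A new one first arising after the window and reported as a non-serious AE is not.

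**Step 3: disposition.** Protocol 8.2 allows an AE as a reason for leaving the study, and SAP 5.1 counts exits by reason. The study-discontinuation AE table admits only TEAEs. If an AE from the last row ended participation, disposition could count the exit while that table omitted the AE term.

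**Step 4: days outside the window, for a subject followed to the end of Week 16.** Let D be the day of last dose, an assumption because the documents do not give it.

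- End of Week 16: 16 × 7 = Day 112
- Off-drug follow-up: 112 − D
- Window closes on day D + 14
- Days outside: 112 − (D + 14) = 98 − D, with a floor of 0

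| D (assumed) | Off-drug days | Days outside | Share |
|---|---|---|---|
| 14 | 98 | 84 | 86% |
| 28 | 84 | 70 | 83% |
| 56 | 56 | 42 | 75% |
| 84 | 28 | 14 | 50% |
| 98 | 14 | 0 | 0% |

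**Step 5: de-escalation.** Under Protocol 4.1, subjects stopping at Dose Level 3 or 4 "should undergo dose de-escalation if appropriate"; the length is redacted. If stopping begins on day S and de-escalation takes e days, then D = S + e and the days outside are 98 − S − e. With S = 56 and e assumed to be 0, 7, 14 or 21, the result is 42, 35, 28 or 21 days. Dose Levels 1 and 2 need no de-escalation. The Sentinel Cohort titration text in Protocol 4.1 tells sites to stop drug in subjects who cannot reach or tolerate Dose Level 2. The gap is therefore widest for the earliest stoppers.

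**Step 6: limits of the formula.** It covers follow-up to Day 112 only. Non-extension subjects have a taper and a safety follow-up period, and withdrawn subjects may return for a later visit. Those lengths are redacted. A gap after a last dose later than Day 98 can be neither shown nor excluded. In the other direction, early exit or the Sponsor's termination shortens every figure above.

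**The case against.** The strongest reply is that this is ordinary elaboration. Protocol 11 calls itself a summary and leaves technical detail to the SAP; Table 9 is silent on an end date and does not promise open-ended counting. A 14-day limit is a sensible rule for on-drug tables, and SAP 7.1 states it openly. SAP 9 signals a reduced, synoptic report. The affected events are few in kind: non-serious, dated, more than two weeks off drug, in a subject who stopped and stayed. Late SAEs and deaths can still be listed, and the DMC reviewed unblinded safety data throughout.

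Much of this stands. It limits the weight of the point and supports keeping the window. It does not answer two things. Announcing selected safety data does not disclose a new cut-off on a definition the protocol states. Adding a cut-off also goes beyond detail when no output is named for the events it removes.

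The reply is also right on three narrower matters. SAP 7.1 does not say that its set of listings is exhaustive, so the finding is that no named output shows these events. Protocol 8.1 lets later visits be remote, so the documents do not establish that laboratory tests or ECGs are done at all of them. The disposition mismatch is hypothetical: an AE starting inside the window that later causes exit is already in the table, and no late AE-driven exit is documented.

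**Conclusion.** The point holds as a reporting gap and an undeclared change of definition. SAP 7.1 narrows protocol Table 9, SAP 9 does not say so, and a collected non-serious AE with known onset more than 14 days after the last dose appears in no named AE output. SAP 7's assurance about abnormal results does not hold for new abnormalities first arising in that time.

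For a subject followed to Day 112, at most 98 − D days are affected. How many subjects stopped early and stayed is not in the documents and lies between 0 and 8.

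A reader might infer that the TEAE percentages are biased, or that most post-drug safety data are lost. The documents support neither. The 14-day tables are valid for what they measure, serious and fatal events can still be listed, and the 50% to 86% shares are upper bounds on assumed stopping days. Nor does Day 98 mark a point after which no gap can exist, since the later follow-up lengths are redacted. The change is worth making because it is cheap, with no claim that a known event has been missed.

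**What to change.** - Keep the 14-day window for the TEAE tables, and state in SAP 9 that it changes the definition in protocol Table 9.
- Add one listing, with a count by arm, of all AEs starting more than 14 days after the last dose. Label it off-drug, and show days since last dose and medications started after stopping. If there are none, print an empty listing that says so, as SAP 7.1 already does for its other listings.
- In the table of AEs leading to study discontinuation, include such AEs whatever their onset after first dose and mark the off-drug ones, so that it agrees with SAP 5.1.

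The cost is one SAP sentence, one listing and one table rule before database lock. Onset dates, exit reasons and medications are already collected, and no protocol amendment is needed. If the database is already locked, SAP 4.1 allows a post hoc listing described in the clinical study report. The downside is that off-drug events may be confounded by medications that Protocol 8.1 permits once drug is stopped, so the new listing and its counts should be kept apart from the TEAE tables.

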8.1. Discontinuation of Study Treatment

If a subject prematurely discontinues study treatment dosing, the investigator will record the reason for discontinuation on the relevant eCRF. Such subjects will not be automatically withdrawn from the study and should continue participation. Data for any outcome measures, particularly the primary and secondary endpoints, as well as safety follow-up, are important to collect. PK sampling is not required after study treatment has been discontinued; however,

subjects should return to the study center at the next scheduled visit for safety assessments. Additional study visits and assessments for subjects who discontinue study treatment but agree to remain in the study may be conducted remotely. Medications listed in [Section 7.1](#) are no longer prohibited after study treatment discontinuation.

Reasons for discontinuation from study treatment include but are not limited to:

- Withdrawal by subject
- Death
- Lost to follow-up
- Site termination by the Sponsor
- Study termination by the Sponsor
- AE
- Pregnancy
- Lack of efficacy
- Protocol deviation

The investigator must discontinue study treatment dosing if the subject experiences any of the following:

- If the type, frequency, or severity of any AE becomes unacceptable/intolerable. This includes AEs of seizures. Criteria for evaluating whether seizures should be considered AEs are provided in [Section 10.1](#).
- A clinically significant worsening in the underlying seizure disorder requiring an adjustment in concomitant ASM regimen to ensure subject safety, including increased usage of rescue medication.
- If the subject is unable to tolerate Dose Levels 1 or 2 for the assigned weight group.
- QTcF of >500 msec (cardiologist verified) on any ECG tracing.
- QTcF change from baseline >60 msec (cardiologist verified) and confirmed with repeated ECG measure.
- If the subject exhibits suicidal behavior, or suicidal ideation of type 4 (active suicidal ideation with some intent to act, without specific plan) or type 5 (active suicidal ideation with specific plan and intent) based on the C-SSRS.
- If the subject is confirmed to be pregnant.
- Withdrawal of consent/assent for study treatment administration by parent/caregiver or subject.

It is crucial to obtain follow-up data for any subject who discontinues study treatment dosing because of an AE, abnormal laboratory test, vital sign measurement, physical examination, or ECG finding. In any case, every effort must be made to undertake safety follow-up procedures.

